9.3.2 Safety and effectiveness outcomes

For each outcome, potential cases will be identified using diagnostic Read codes ([Annex 3](#)) and, where appropriate, computerized patient profiles (including any free text comments) will be reviewed with all identifying information removed. Diagnostic confirmation using patients' original medical records will be performed where possible. When required, information contained in HES among the subset of practices linked to THIN, will be used.

For the purpose of this study, clinically relevant bleedings will be defined as bleedings leading to hospital admission or referrals to a specialist. This restriction is needed to minimize differential misclassification caused by the variability in patients' behavior in seeking care for less severe bleedings. Similarly, the physicians' attitude towards recording these events may differ between new drugs and standard of care. The consequence of restricting to bleedings identified through hospitalization or referrals is that bleedings leading to death before contact with a health care professional or hospital admission might be missed. It is assumed that the number of bleeding events missed due to this restriction is small. Nevertheless, the magnitude and impact of this restriction will be assessed in another study of this PASS program (Swedish Record-linkage study).

9.3.2.1 Occurrence of intracranial haemorrhage, gastrointestinal bleeding and urogenital bleeding: case definitions

Intracranial haemorrhage (Annex 3, Table 4)

Cases of intracranial haemorrhage will be identified in patients referred to a specialist or admitted to hospital that meet the criteria for one of the three following categories:

- incident cases of intracerebral haemorrhage recorded following or in association with computed tomography, magnetic resonance imaging (MRI) or X-ray angiography, or an appropriate therapeutic procedure.
- incident cases of subarachnoid haemorrhage recorded following computed tomography, MRI, X-ray angiography or lumbar puncture, or an appropriate therapeutic procedure.
- incident cases of epidural, dural, subdural and arachnoid haemorrhage recorded following computed tomography, MRI, X-ray angiography or lumbar puncture, or an appropriate therapeutic procedure.

Gastrointestinal bleeding (Annex 3, Table 5)

A patient will have to meet the following criteria to be considered a case of gastrointestinal bleeding:

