- the specific site of bleeding originating in the upper or lower gastrointestinal tract or, more specifically, in the oesophagus, stomach, duodenum, jejunum, ileum, colon or rectum.
- for upper gastrointestinal bleeding, the lesion type being erosion, gastritis, duodenitis or peptic (gastric or duodenal) ulcer.
- the lesion type being NOT related to cancer.
- the patient having been referred to a specialist or admitted to hospital.

Urogenital bleeding (Annex 3, Table 6)

A patient will have to meet both of the following criteria to be considered a case of urogenital bleeding:

- the specific site of bleeding originating in the urogenital tract.
- the patient having been referred to a specialist or admitted to hospital.

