9.7.2 Safety and effectiveness outcomes

The two cohorts (of first-time users of rivaroxaban and first-time users of comparators) will be followed up from the index date until 12 months after the end of the enrolment period for potential outcomes (safety and effectiveness). For each outcome, the first referral or hospitalization for that

outcome during the follow-up period will be identified. A separate follow-up will be performed for each of the outcomes.

Crude incidence rates will be estimated in both cohorts for DVT/PE treatment, SPAF and ACS. Incidence will be computed using the person–time contribution of the study cohorts, stratified into current, recent, past and non-use. Current use will refer to person–time up to 7 days after the end of supply of the index drug, recent use will refer to person–time up to 90 days after the end of current use, past use will include all person–time contribution after the end of recent use up to 1 year after the end of current use, non-use will include all remaining time person–time contribution after past-use until end of follow-up.

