9.7.2.1 Primary safety outcomes

Crude incidence rates will be estimated for each of the three primary adverse outcomes in both cohorts. Age- and sex-adjusted rate ratios with 95% CIs will be estimated for each of the three primary adverse outcomes comparing rivaroxaban with standard of care using Poisson regression analysis based on person–time contribution (current, recent and past use as defined in [Section 9.7.2](#)).

Where numbers and data permit, adjustment will be made for baseline medication and comorbidity variables described in the drug utilization section, including indication and history of adverse outcomes (referral or hospitalization for haemorrhagic stroke, gastrointestinal bleeding or urogenital bleeding recorded at any time before the index date).

If numbers of final cases permit, estimation of the relative risk among rivaroxaban users will be adjusted for known risk factors of the specific outcome using logistic regression models in nested case-control analyses.

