761Jy00	Other specified operation on gastric ulcer
761Jz00	Operation on gastric ulcer nos
7627	Operations on duodenal ulcer
7627100	Suture of duodenal ulcer not elsewhere classified
7627y00	Other specified operation on duodenal ulcer
7627z00	Operation on duodenal ulcer nos
G850.00	Oesophageal varices with bleeding
G852000	Oesophageal varices with bleeding in diseases EC
G852100	Oesophageal varices without bleeding in diseases EC
J10y000	Haemorrhage of oesophagus
J107.00	Mallory-Weiss syndrome
J108.00	Mallory - Weiss tear
J573.00	Haemorrhage of rectum and anus
J573000	Rectal haemorrhage
J573011	Rectal bleeding
J573012	PRB - Rectal bleeding
J573100	Anal haemorrhage
J573.11	Bleeding PR
J573z00	Haemorrhage of rectum and anus NOS
J510900	Bleeding diverticulosis
J573.00	Haemorrhage of rectum and anus
J573000	Rectal haemorrhage

C/O, complaint of; EC, elsewhere classified; GIB; gastrointestinal bleeding; H/O, history of; LOC, loss of consciousness; O/E, on examination; NEC, not elsewhere classified; NOS, not otherwise specified; PR, per rectum; PRB, per rectal bleeding.

Table 6. Read codes for urogenital bleeding.

Read code	Description
14D5.00	H/O: haematuria
1A45.00	Blood in urine - haematuria
1A45.12	Haematuria - symptom
K032100	Recurrent benign haematuria syndrome
K0A2.00	Recurrent and persistent haematuria
K0A2000	Recurrent+persistnt haematuria minor glomerular abnormality
K0A2100	Recur+persist haematuria
K0A2200	Recur+persist haematuria difus membranous glomerulonephritis
K0A2300	Recur+persist haemuria df mesangial prolif glomerulonephritis
K0A2400	Recur+persist haemuria df endocaply prolifrtv glomeruloneph
K0A2500	Recur+persist hmuria df mesangiocapillary glomerulonephritis
K0A2600	Recurrent and persistent haematuria
K0A2700	Recur+persist haematuria difus crescentic glomerulonephritis
K197.00	Haematuria
K197.11	Traumatic haematuria
K197.12	Essential haematuria
K197000	Painless haematuria
K197100	Painful haematuria
K197200	Microscopic haematuria
K197300	Frank haematuria
K197400	Clot haematuria
K53y600	Haematosalpinx
K544.00	Haematometra
K595.11	Intermenstrual bleeding - regular
K596.00	Metrorrhagia
K596.11	Intermenstrual bleeding - irregular
K597.00	Postcoital bleeding
K59A.00	Premenopausal postcoital bleeding
K59B.00	Postmenopausal postcoital bleeding
K59y.11	Metropathia haemorrhagica
K59y000	Retained menstruation
K59yx00	Dysfunctional uterine haemorrhage NOS
K59yx11	Dysfunctional uterine bleeding
K59yy00	Functional uterine haemorrhage NOS

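### Gastrointestinal and urogenital bleeding cases need not be new episodes, so a referral or admission that continues a pre-index bleed can count against the newly started drug

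*Protocol*

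**What the plan says.** **Counting rule (9.7.2).** Both cohorts "will be followed up from the index date until 12 months after the end of the enrolment period for potential outcomes". There is no lag and no bleed-free run-in. The event is defined by "For each outcome, the first referral or hospitalization for that" outcome within that window.

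**Case definitions (9.3.2.1).** Intracranial haemorrhage has three categories, and each asks for incident cases; the first reads "incident cases of intracerebral haemorrhage recorded following or in association with computed tomography". Gastrointestinal bleeding is defined by site, by lesion type for upper bleeds, by "the lesion type being NOT related to cancer", and by "the patient having been referred to a specialist or admitted to hospital". For urogenital bleeding, "A patient will have to meet both of the following criteria to be considered a case of urogenital bleeding": the site, and a referral or admission. Neither definition mentions onset, first record or a new episode.

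**Adjustment (9.7.2.1).** The committed adjustment is for age and sex. Further adjustment, including for a history of referral or hospitalization for haemorrhagic stroke, "gastrointestinal bleeding or urogenital bleeding recorded at any time before the index date", is made only if numbers and data allow.

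**Sensitivity analyses (9.7.2.7).** These are planned around the start and stop of treatment, motivated by the different onset and offset of the drugs.

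**Entry (9.1).** Earlier users of the index drug are excluded. Earlier users of another anticoagulant may enter as non-naïve patients, and those exposed to the other drug within 6 months before the index date are recent switchers.

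**The concern.** The start of a new drug and the start of a bleed are separate events, and a specialist referral or an admission can follow a bleed by some time. If the bleed comes first, the drug is then changed, and the referral or admission follows the change, the contact falls in follow-up on the new drug although the bleed arose before it. Counting contacts from the index date, without asking when the episode began, attributes that bleed to the wrong treatment.

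Two of the three primary safety outcomes are exposed. If carry-over were proportionally equal in the two cohorts, the rate ratio would not move. If it were more common among rivaroxaban starters, for instance because bleeding on warfarin prompts some switches, the ratios would be biased upwards, mostly early in follow-up. In a safety study that could look like a signal.

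**Working it through.** **1. The plan's own figure.** Section 9.5 gives 5 haemorrhagic strokes per 1000 person-years and 12,000 and 48,000 person-years, to exclude a 50% increase with 80% power. Expected events are 60 and 240. SE = √(1/60 + 1/240) = 0.1443. With a true ratio of 1 and a two-sided 5% level (assumed from the planned 95% intervals), power = Φ(ln 1.5/0.1443 − 1.96) = Φ(0.85) = 80.2%. The figure reproduces. It concerns haemorrhagic stroke, where cases must be incident, so this point does not touch it.

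**2. A patient traced through the rules.** A patient on warfarin since before enrolment has haematuria recorded by the primary care practitioner, is switched to rivaroxaban, and is then referred for that haematuria.
- Entry: no earlier rivaroxaban, so eligible; a recent switcher.
- Site: urogenital, met.
- Referral or admission: met.
- First such contact in follow-up: met.

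The result is a urogenital event on current rivaroxaban use. Under the intracranial wording, the same sequence could be rejected as not incident. The Annex 3 list of potential urogenital cases includes "Recurrent and persistent haematuria", a description that fits a continuing condition as readily as a new one.

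**3. Direction from the entry rules (9.1).**
- On warfarin before enrolment, later switched: barred from the warfarin cohort, admitted to the rivaroxaban cohort. Carry-over falls on rivaroxaban.
- Starts warfarin during enrolment, bleeds, switches: stays in the warfarin cohort. No carry-over to rivaroxaban.
- Starts rivaroxaban during enrolment, later moves to warfarin: stays in the rivaroxaban cohort. No mirror image.
- Starts warfarin after another anticoagulant, or with a bleed already under way: carry-over can fall on warfarin.

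The rules lean towards rivaroxaban but do not settle the net effect.

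**4. Illustrative size.** The protocol gives no gastrointestinal or urogenital rate, no switcher share and no share switching after a bleed. Apart from the 12,000 person-years, every input here is assumed, and carry-over is placed in the rivaroxaban cohort alone.
- True events, both outcomes together: 12,000 × 20/1000 = 240.
- False events = starters × switcher share × share with a recent referred bleed × share with a follow-on contact.
- Low: 10,000 × 0.20 × 0.01 × 0.30 = 6. Ratio 1 + 6/240 = 1.025.
- Middle: 10,000 × 0.25 × 0.025 × 0.40 = 25. Ratio 1 + 25/240 = 1.10.
- High: 10,000 × 0.30 × 0.04 × 0.50 = 60. Ratio 1 + 60/240 = 1.25.

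A wider set of guesses (switchers 10% to 50%, recent bleed 2% to 10%, follow-on contact 25% to 50%, 10 events per 1000 person-years, one year per patient) adds 0.5 to 25 cases per 1000 patients, for ratios of 1.05 to 3.5. That spread shows how little the documents pin down.

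**5. What modest carry-over would do to one outcome.** At an assumed 10 per 1000 person-years, true events are 120 and 480. With 10% carry-over on rivaroxaban only, 132 and 480: SE = √(1/132 + 1/480) = 0.0983, and the chance that the 95% interval lies wholly above 1 is Φ(ln 1.1/0.0983 − 1.96) = Φ(−0.99) = 16%, against 2.5% with none. For 5%, 20% and 30% it is 7%, 48% and 81%. If warfarin carries 5% while rivaroxaban carries 10%, the ratio is 1.10/1.05 = 1.048 and the chance is 7%. With the same percentage in both, the ratio is 1.00.

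**The case against.** **Adjustment may deal with it.** A carried-over patient with an earlier referred bleed is positive on the bleeding-history covariate. If follow-on contacts are equally frequent among earlier bleeders in both cohorts and only the share of earlier bleeders differs, adjustment removes much of the distortion. This stands in part. The adjustment is conditional, and its any-time look-back mixes remote bleeds with those just before the switch. The carried-over contact also remains a counted event.

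**Early-treatment analyses exist.** Section 9.7.2.7 addresses the start of treatment, and says that biases recognized in the drug-utilization data can be accounted for later. This also stands in part: those analyses could expose an early excess, but they are not a rule on new versus continuing bleeds.

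**Case review could catch it.** Profiles, free text and questionnaires (9.3.2, 9.8) may well show that a bleed preceded the index date, and the stated measure is incidence. It would be too strong to say that review cannot reject such cases. However, no listed criterion tells the reviewer to do so.

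**This may be analysis-plan detail.** A look-back length may be. The criteria that a case must meet are set in the protocol, and differ across its three primary outcomes.

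**The direction is inferred.** This stands. A reader might infer that the rivaroxaban ratios will be inflated by a stated amount. The documents do not support that: they give no reasons for switching and no counts. The main route is limited to patients on warfarin before enrolment, and warfarin starters can carry bleeds over too.

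**Conclusion.** The gap is documented. For gastrointestinal and urogenital bleeding, a contact after the index date for a bleed that began before it satisfies every stated criterion and is attributed to the new drug; the intracranial definition guards against this in words. Existing provisions reduce the problem without closing it.

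Bias against rivaroxaban is plausible from the entry rules, but neither its direction nor its size is established. The range of 1.03 to 1.25 rests wholly on assumed rates and shares and on no carry-over in the warfarin cohort; its low end is negligible. Intracranial haemorrhage and the stated study size are unaffected. The protocol should be corrected because the repair is cheap and two primary outcomes depend on it, not because a bias has been demonstrated.

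**What to change.** In 9.3.2.1, add to the gastrointestinal and urogenital definitions that the case must be an incident episode whose first record falls after the index date, in line with intracranial haemorrhage. State that case review rejects contacts for a bleed documented before the index date, with the same rule in both cohorts. A new bleed after the index date in a patient with an earlier bleed still counts.

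Add two sensitivity analyses: (a) without this rule, and (b) excluding early person-time in patients who had a referred or hospitalized bleed at the same site shortly before the index date. A window of 90 days is one example for (b); it is an assumption with no source in the protocol. This exclusion should not be the main analysis, because it would also drop genuine re-bleeds on the new drug and early time at risk.

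The cost is slightly more review work and a few fewer counted events. If carry-over is negligible, analysis (a) will show it.

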9.7.2.1 Primary safety outcomes

Crude incidence rates will be estimated for each of the three primary adverse outcomes in both cohorts. Age- and sex-adjusted rate ratios with 95% CIs will be estimated for each of the three primary adverse outcomes comparing rivaroxaban with standard of care using Poisson regression analysis based on person–time contribution (current, recent and past use as defined in [Section 9.7.2](#)).

Where numbers and data permit, adjustment will be made for baseline medication and comorbidity variables described in the drug utilization section, including indication and history of adverse outcomes (referral or hospitalization for haemorrhagic stroke, gastrointestinal bleeding or urogenital bleeding recorded at any time before the index date).

If numbers of final cases permit, estimation of the relative risk among rivaroxaban users will be adjusted for known risk factors of the specific outcome using logistic regression models in nested case-control analyses.

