- The prevention of stroke and systemic embolism in adult patients with non-valvular atrial fibrillation (stroke prevention in atrial fibrillation [SPAF]) with one or more risk factors, such as congestive heart failure, hypertension, age \geq 75 years, diabetes mellitus, prior stroke or transient ischaemic attack (20 mg rivaroxaban od).
- The prevention of venous thromboembolism (VTE) in adult patients undergoing elective hip or knee replacement surgery (recommended dose: 10 mg rivaroxaban od for 35 days following hip replacement surgery and 14 days following knee replacement surgery).
- Co-administered with acetylsalicylic acid (ASA) alone or with ASA plus clopidogrel or ticlopidine, for the prevention of atherothrombotic events in adult patients after an acute coronary syndrome (ACS) with elevated cardiac biomarkers (recommended dose 2.5 mg bid).

As is the case with other anticoagulants, clinical studies of rivaroxaban have identified haemorrhage as an important safety outcome ([Lassen, Ageno et al. 2008](#); [Turpie, Lassen et al. 2009](#)). A post-authorization safety study programme is planned for several European countries. This document summarizes the design of a population-based study to characterize new users of rivaroxaban, assess patterns of drug utilization, including adherence to label recommendations, and to assess the risk of bleeding associated with rivaroxaban treatment compared with the standard of care in routine clinical practice in the UK, for ACS, DVT/PE treatment and SPAF. For DVT/PE treatment and SPAF, standard of care is treatment with the most widely used vitamin K antagonist, warfarin, and for the secondary prevention of ACS, standard of care is antiplatelet drug(s) such as low-dose acetylsalicylic acid, clopidogrel, dipyridamole, prasugrel, ticlopidine and ticagrelor.

8 Research questions and objectives

This post-authorization study was designed to assess patterns of drug utilization and to quantify outcomes related to safety and effectiveness in new users of rivaroxaban compared with new users of standard of care.

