8.1.2 Safety and effectiveness outcomes

- To study the occurrence of hospitalization or referral to a specialist from primary care for three bleeding events (primary safety outcomes): (a) intracranial haemorrhage, (b) gastrointestinal bleeding and (c) urogenital bleeding among users of rivaroxaban (for DVT/PE treatment, SPAF and ACS) in comparison with individuals receiving current standard of care.

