9.1 Study design

This study has a cohort design including nested case–control analyses.

Cohorts of first-time users of either rivaroxaban or comparators will be identified using the date of first prescription (index date) of the respective drug (index drug) (Figure 1).

A patient will be considered eligible to enter the study cohort as a first-time user of rivaroxaban or a first-time user of “standard of care” when he or she has a first prescription of the drug recorded during the enrolment period. In the UK, for VTE prevention, DVT/PE treatment and SPAF, standard of care is treatment with the most widely used vitamin K antagonist, warfarin, and for the secondary prevention of ACS, standard of care is antiplatelet drug(s) such as low-dose acetylsalicylic acid, clopidogrel, dipyridamole, prasugrel, ticlopidine and ticagrelor.

Patients who have any record of being prescribed their index drug prior to the enrolment period or who qualify as members of both cohorts on the same day, will be excluded. If a patient qualifies as first-time user of both rivaroxaban and “standard of care” comparison drug during the enrolment period, she/he will be assigned to the cohort of drug first prescribed during the enrolment period, with the date of this prescription being the index date.

Many patients with ACS have a history of ischaemic heart disease for which platelet inhibition is standard treatment, and thus exclusion of patients with prior use of platelet inhibitors risks excluding a majority of typical ACS patients. Therefore, those who have been using one or more platelet inhibitors will remain eligible to enter the study.

Standard of care for ACS patients is combination therapy, and as such cohort assignment will be based on first use of rivaroxaban (in combination with aspirin or clopidogrel, or multi-antiplatelet therapy), or use of aspirin and clopidogrel and/or other antiplatelet medications.

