9.5 Study Size

All patients enrolled in THIN and meeting the inclusion criteria will be included. The size of the population receiving rivaroxaban will be dependent on market uptake across the indications of interest (DVT/PE treatment, ACS and SPAF).

According to a preliminary sample size calculation, based on an incidence of haemorrhagic stroke in warfarin-treated patients of 5 per 1000 person-years, 12,000 rivaroxaban-treated patient-years and 48,000 warfarin-treated patient-years would be required to exclude a 50% increased risk of haemorrhagic stroke in rivaroxaban-treated patients compared with warfarin-treated patients with a power of 80%.

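### The only rate ratio guaranteed for the primary outcomes spans two different comparators with indication adjustment optional, so it is open to confounding by indication

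*Protocol*

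**What the plan says.** The primary safety objective in section 8.1.2 covers three indications at once: bleeding "among users of rivaroxaban (for DVT/PE treatment, SPAF and ACS) in comparison with individuals receiving current standard of care".

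The comparator depends on the indication. Section 9.1 states that "for VTE prevention, DVT/PE treatment and SPAF, standard of care is treatment with the most widely used vitamin K antagonist, warfarin". The same section, like section 7, makes antiplatelet drugs the comparator in ACS, and it assigns ACS patients to the rivaroxaban cohort when rivaroxaban is taken together with antiplatelet therapy.

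For the outcome analysis, section 9.7.2.1 says "Age- and sex-adjusted rate ratios with 95% CIs will be estimated for each of the three primary adverse outcomes comparing rivaroxaban with standard of care", by Poisson regression. Indication comes in afterwards, as a conditional covariate: "Where numbers and data permit, adjustment will be made for baseline medication and comorbidity variables described in the drug utilization section, including indication". Sections 9.7.2.2 to 9.7.2.4 repeat the conditional adjustment for the secondary outcomes without naming indication. Section 9.7.2 promises crude incidence rates for DVT/PE treatment, SPAF and ACS, but no rate ratio by indication or by comparator.

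Section 9.5 sizes the study to "exclude a 50% increased risk of haemorrhagic stroke in rivaroxaban-treated patients compared with warfarin-treated patients".

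**The concern.** Two separate problems follow.

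- **Confounding by indication.** If ACS makes up a different share of person-time in the two cohorts, and its bleeding rate differs from that of the warfarin indications, a ratio adjusted only for age and sex can depart from 1 even when rivaroxaban has no effect in any indication.
- **No single parameter.** In DVT/PE and SPAF the contrast is one anticoagulant against another. In ACS it is an anticoagulant added to antiplatelet therapy against antiplatelet therapy alone. If the two true ratios differ, a combined ratio is an average whose weights follow market uptake. Adjusting for indication does not change that.

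At stake is the primary safety estimate of a post-authorization safety study, and its link to the warfarin comparison for which the study was sized.

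**Working it through.** **1. The plan's own figure.** Inputs from section 9.5: 5 events per 1000 person-years, 12,000 and 48,000 patient-years, ratio 1.5 to be excluded, 80% power. The section gives no alpha; two-sided 5% is assumed, in line with the 95% intervals.
- Expected events under a true ratio of 1: 12,000 × 0.005 = 60 and 48,000 × 0.005 = 240.
- SE of the log ratio = √(1/60 + 1/240) = 0.144.
- Power = Φ(ln 1.5 / 0.144 − 1.96) = 80.2%.

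The stated size is reproduced, for the warfarin contrast.

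**2. Ratio with indication left out.** The protocol gives no ACS shares and no ACS bleeding rate, so these are assumptions. Take a true ratio of 1 in every indication, and 20 (warfarin indications) and 10 (ACS) events per 1000 person-years. Let s be the ACS share of a cohort's person-time. The cohort rate is (1 − s) × 20 + s × 10.

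| ACS share, rivaroxaban | ACS share, comparator | Calculation | Ratio |
|---|---|---|---|
| 2% | 40% | 19.8 / 16.0 | 1.24 |
| 20% | 2% | 18.0 / 19.8 | 0.91 |
| equal | equal | same rate in both | 1.00 |

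With the protocol's 5 per 1000 for the warfarin indications, and ACS shares of 2–20% (rivaroxaban) and 2–60% (comparator), the ratio runs from 0.91 to 1.41 at an assumed ACS rate of 2.5 per 1000. At 1 per 1000 it runs from 0.85 to 1.89. If the ACS rate is also 5 per 1000, it is 1.00 throughout. These are unadjusted ratios; age and sex adjustment is not modelled.

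**3. Ratio with indication in the model.** If the true ratio is 1 in both strata, the indication-adjusted Poisson ratio is 1.00, so the distortion in step 2 disappears. Now assume ratios of 0.8 against warfarin and 2.0 against antiplatelets, comparator rates of 5 and 2.5 per 1000, 12,000 and 48,000 person-years, and ACS at 40% of comparator time. The adjusted ratio θ solves Σ R = Σ T × θP / (θP + C). R is rivaroxaban events, T all events, and P and C are rivaroxaban and comparator person-years, by stratum.
- Rivaroxaban ACS share 2%: rivaroxaban events 47.04 and 1.2, comparator events 144 and 48; θ = 0.82.
- Rivaroxaban ACS share 50%: rivaroxaban events 24 and 30, comparator events 144 and 48; θ = 1.18.

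The underlying effects are the same in both rows. Only the mix has changed, and the answer crosses 1.

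**4. Cost in precision of separating.** If a comparison holds half the planned person-years in both arms, events are 30 and 120, SE = √(1/30 + 1/120) = 0.204, and power = Φ(0.405 / 0.204 − 1.96) = 51%. At a 75% share it is 68%. At 25% and 10%, with the same event rate, it is 29% and 14%.

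**The case against.** The strongest reply is that section 9.7.2.1 never says the indications are pooled. Section 9.1 gives ACS its own assignment rule, Figure 1 subdivides only the DVT/PE and SPAF cohorts, and an indication covariate would also make sense in a model confined to those two. A statistical analysis plan, not at hand, might stratify. There are partial safeguards too. Crude rates by indication will be shown. Section 9.7.1 compares baseline characteristics by indication. Section 9.7.2.7 allows biases found there to be accounted for in the outcome analyses. At the planned size, 60 + 240 = 300 haemorrhagic strokes would support a covariate with two or three levels, and the Annex 2 checklist records no a priori hypothesis, so no decision rule hangs on the ratio.

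Much of this stands. Pooling is implied, not stated, and the distortion in step 2 of the working arises only if indication is left out. The reply does not remove the point, because the protocol is not silent here. It fixes one ratio for an objective that names all three indications, and it makes control of the variable that determines the comparator optional. Where stratification by indication is intended, as for the odds ratios in section 9.7.1, the text says so; the outcome sections do not. Crude rates by indication are unadjusted and do not replace a ratio. Section 9.6 describes running several multivariable models after the crude analysis before choosing the final one, so whether indication enters could be decided late.

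**Conclusion.** The point holds in a limited form. The one rate ratio that the protocol guarantees implicitly combines a warfarin contrast with an antiplatelet contrast and is open to confounding by indication. Without indication adjustment, the illustrative ratios under no true effect are 1.24, 0.91 or 1.00, depending wholly on assumed ACS shares and bleeding rates. Indication adjustment removes this if the ratio is common to all indications. If it differs by comparator, no single interpretable parameter results.

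A reader might go further in three ways that the documents do not support.
- That the estimate is confounded, with a false excess for rivaroxaban. Neither the indication mix nor an ACS bleeding rate is given, and the distortion can go either way or vanish.
- That ACS time enters only the comparator side. ACS is also an indication in the rivaroxaban cohort, and ACS time brings events as well as person-years.
- That the sample size is wrong. It reproduces, and section 9.5 already names warfarin as the comparator. It simply does not speak for ACS or for each indication.

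**What to change.** - In sections 9.7.2.1 to 9.7.2.4, estimate rate ratios separately by comparator: DVT/PE treatment and SPAF against warfarin, always stratified by or adjusted for indication; and ACS against antiplatelet drugs.
- Label any figure pooled over ACS as secondary.
- In section 9.5, add that the 80% power refers to the combined warfarin-comparator contrast, not to each indication or to ACS.
- Bring the data analysis paragraph of the abstract into line.

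The cost is wording; indication is already collected under section 9.3.1. The statistical downside is wider intervals within each comparator or indication. The 80% is kept for the warfarin comparison if the full 12,000 and 48,000 patient-years are warfarin-indication time, and falls to about 51% at half of them.
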